8.1.4 Events of Special Interest

ESIs will be monitored over time by the independent DSMB, as described in the DSMB charter, regardless of whether these events were reported as AEs. Any events that qualify as an AE or SAE will be reported accordingly (see [Sections 8.1, 8.2, and 8.3](#)).

ESIs will include the following hepatic abnormalities, muscle-related abnormalities, new-onset diabetes mellitus (NODM) and/or hyperglycemia, renal abnormalities, changes to antihypertensive medication(s) due to changes in blood pressure, and ophthalmic events (ie, macular degeneration), described as follows:

- AST or ALT $>3 \times$ ULN;
- Bilirubin $>2 \times$ ULN;
- CK $>5 \times$ ULN;
- NODM or worsening of glycemic control;

Note: NODM is defined by 1 or more of the following criteria, based upon information from AE, medication, and laboratory data:

- AE indicating new type 1 or type 2 diabetes;
- Initiation of anti-diabetes medication with confirmation of the diagnosis of diabetes by blinded external review by experts in diabetology;
- HbA1c $\geq 6.5\%$ (≥ 0.065 hemoglobin fraction); and/or
- Two consecutive values of fasting plasma glucose that are ≥ 126 mg/dL (≥ 7.0 mmol/L).

Note: Worsening of glycemic control will be defined as an HbA1c increase from Baseline $>0.5\%$ (>0.005 hemoglobin fraction) and/or a new concomitant medication or increase in current antidiabetic therapy in a participant with a Baseline HbA1c $\geq 6.5\%$ (≥ 0.065 hemoglobin fraction).

- A >25% decrease in eGFR from Baseline or an eGFR <30 mL/min/1.73 m², calculated using the Chronic Kidney Disease Epidemiology Collaboration equation, and/or an increase in serum creatinine of ≥ 0.3 mg/dL (≥ 26.5 μ mol/L) from Baseline;
- Changes to antihypertensive medication(s) due to changes in blood pressure in those participants receiving antihypertensive medication(s) treatment at Baseline; and
- Macular degeneration.

These ESIs will be monitored through review of the AE and laboratory database.

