8.1.4.5 Guidelines for monitoring and management of changes to antihypertensive medication(s)

Any changes to antihypertensive medication(s) due to changes in blood pressure in those participants receiving antihypertensive medication(s) treatment at Baseline will be assessed by the Investigator, primary care physician, or other appropriate health care provider to assess for etiologies of blood pressure change, to confirm clinical safety of the participant, to assess the need for any AE or SAE reporting, and to arrange for appropriate medical follow-up.

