Participants will be identified as those who had a diagnosis of hypertension in their medical history and received antihypertensive medication(s) at Baseline. If participants had an adverse event related to hypertension after Baseline (see [Appendix B](#) for preferred terms) and had any change in antihypertension medication within 30 days of the start date of the adverse event, that change

in antihypertension medication will be considered as due to a change in blood pressure. The number and percentage of participants will be summarized by treatment group.

Participants will be identified who did not have a prior diagnosis of hypertension in their medical history and did not receive antihypertensive medication(s) at Baseline. If participants had an adverse event of hypertension and initiated antihypertension medication within 30 days of the start date of the adverse event, the adverse event will be classified as a change in blood pressure. The number and percentage of participants will be summarized by treatment group.

Cases of macular degeneration will be recorded and summarized using the appropriate system organ class. These events will be summarized by severity and relationship to study drug for each treatment group.

3.5.3 *Clinical Laboratory Tests*

Blood and urine samples for clinical laboratory evaluations (including a full serum chemistry panel, hematology, coagulation, and urine dipstick analysis) will be collected at visits specified in [Table 1](#). A limited serum chemistry panel will also be collected as specified in Table 1. All safety laboratory samples should be collected while the participant is fasting (a minimum of 8 hours) and prior to the next dose of study drug (at applicable visits). Urinalysis will be performed locally by dipstick analysis from a sample of mid-stream urine. See clinical protocol ([Appendix B](#)) for a complete list of analytes.

Laboratory values will be summarized descriptively, including the change from Baseline. In addition, shift tables for all parameters will be presented to describe the change in laboratory parameter values at end of treatment visit using normal range categories (low, normal, and high).

Chemistry and hematology laboratory parameters will be listed.

3.5.4 *Vital Signs*

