Vital signs (heart rate and blood pressure) measured in triplicate prior to study administration at applicable visits as indicated in Table 1. Values will be summarized with descriptive statistics, including the change from Baseline at each visit by treatment group and overall.

Additional summaries of blood pressure measurements will be performed, within treatment group and time point, using counts of triplicate means that meet the following criteria:

- Systolic blood pressure:
 - ≥ 160 mmHg
 - ≥ 180 mmHg
 - change from Baseline by ≥ 20 mmHg
- Diastolic blood pressure:
 - ≥ 100 mmHg
 - ≥ 110 mmHg
 - change from Baseline by ≥ 15 mmHg.

As described above, the number and percentage of participants receiving antihypertensive medications at Baseline with changes to antihypertensive medications due to change in blood pressure will be summarized by treatment group. The number of participants who were not hypertensive or on any antihypertensive medications at Baseline, but started one or more antihypertensive drugs during the treatment period, will be summarized by treatment group.

Vital signs will be listed.

3.5.5 *Electrocardiograms*

A single 12-lead ECG will be performed at Visit 2 and Visit 7/EOT/ET and will be read locally.

ECG parameters will be recorded as normal, abnormal or not done. Abnormal values will be assessed as clinically significant or not clinically significant. Counts and percentages for ECG parameters will be summarized by treatment group and in total.

3.5.6 *Physical Examinations*

Physical examinations (with focused examination on general, respiratory, CV, abdominal, and extremities evaluations) and recording of weight and height will be performed at Screening Visit and Visit 7/EOT/ET. Height will be measured at Screening Visit only and used to calculate body mass index. BMI will be calculated as weight/(height/100)² (kg/m²); rounded and displayed to 1 decimal place.

Physical examination, parameters, will be recorded as normal, abnormal or not done. Abnormal values will be assessed as clinically significant or not clinically significant. Count and percentages for physical parameters will be summarized by treatment group and in total.

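### SAP 3.5.2 adds an undeclared adverse-event condition to the antihypertensive-change event of special interest for participants treated at Baseline

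*SAP*

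**What the plan says.** Protocol 8.1.4 lists, as an ESI, changes to antihypertensive medication caused by changes in blood pressure in participants receiving such medication at Baseline. It says the DSMB monitors ESIs "regardless of whether these events were reported as AEs". It also says "These ESIs will be monitored through review of the AE and laboratory database", which leaves concomitant medication data unnamed. Protocol 8.1.4.5 has each such change assessed, among other purposes, "to assess the need for any AE or SAE reporting, and to arrange for appropriate medical follow-up". Protocol 9.2.2.1 plans the number and percentage of participants with such changes by treatment group and mentions no AE.

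SAP 3.5.2 makes this operational. It selects participants who "had a diagnosis of hypertension in their medical history and received antihypertensive medication(s) at Baseline". It then sets the condition "If participants had an adverse event related to hypertension after Baseline", pointing to the preferred terms in its Appendix B, and requires that the participant also "had any change in antihypertension medication within 30 days of the start date of the adverse event". A change meeting these conditions is taken as due to blood pressure, and no other route is given. For participants with neither a hypertension history nor antihypertensives at Baseline, the rule is similar: "If participants had an adverse event of hypertension and initiated antihypertension medication within 30 days of the start date of the adverse event".

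SAP 3.5.4 repeats the summary for participants treated at Baseline by referring back to 3.5.2. It adds an AE-free count of participants neither hypertensive nor treated at Baseline "but started one or more antihypertensive drugs during the treatment period, will be summarized by treatment group", and AE-free summaries of blood pressure values, changes and threshold crossings.

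**The concern.** In the protocol, the medication change is the event and AE reporting is a separate question. In the SAP, a reported AE is a condition for the event to count. The final table would then depend partly on how sites report AEs in people who already have hypertension. Protocol 8.1 keeps a condition present at Screening out of AE reporting unless its severity, frequency or seriousness changes, so for these participants reporting involves judgement.

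The rule is also loose in another way. It accepts a change of any kind near the AE, so reductions and switches are pooled with escalations. Blood pressure is one of the two safety topics that Protocol 9.2.4 names for DSMB monitoring (the other is ESIs), so the ESI table should count what the protocol defined.

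**Working it through.** The documents give no rate, count or power for this ESI, so there is no figure to reproduce. The check is a comparison of text, followed by an illustration on assumed rates.

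**Text**

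1. *Definition.* Protocol 8.1.4 requires treatment at Baseline, a medication change, and blood pressure as the cause. It requires neither an AE nor a recorded hypertension diagnosis.
2. *Planned summary.* Protocol 9.2.2.1 uses the same elements. This is the firmest comparison with SAP 3.5.2, because both describe the final analysis.
3. *AE reporting.* Protocol 8.1.4.5 treats the need for an AE as something to assess after the change. Protocol 8.1 says an abnormal finding should be reported as an AE if it requires an intervention. Together these make an AE likely for many such changes, but not certain.
4. *SAP rule.* SAP 3.5.2 adds three conditions: hypertension in the medical history, an Appendix B AE, and a 30-day link. A participant on antihypertensives without a recorded hypertension diagnosis falls in neither of its two groups, although the protocol ESI includes that participant.
5. *Direction.* The ESI covers changes in pressure either way. Appendix B has 23 terms. Six are neutral in direction (five of the abnormal type, plus labile blood pressure) and none denotes low pressure. A reduction made for low pressure can qualify only through a neutral term or a nearby hypertension AE.
6. *Declaration.* SAP section 6 lists four changes from the protocol: removal of the word fasting, subgroup analyses, added trough levels, and unequal variances. The AE condition is not among them.
7. *Parallel ESI.* In the same SAP section, worsening of glycemic control can be met by new or increased antidiabetic therapy, with no AE needed.
8. *Other outputs.* The AE-free new-starter count in SAP 3.5.4 excludes anyone treated at Baseline. SAP 3.3.6 tabulates medications taken, not changes. Blood pressure summaries need not show a rise that was already treated by the next visit.

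**Illustration (all rates assumed)**

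Randomization of 300 at 2:1 gives 200 and 100. Assume 30% to 50% are on antihypertensives at Baseline: 60 to 100 on obicetrapib and 30 to 50 on placebo. Assume true pressure-driven changes in 10% versus 5%. Let c be the share that also carries a qualifying AE within 30 days. Expected count = n × rate × c. With equal c in both arms, the counted risk difference is (10 − 5) × c points.

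| c | Obicetrapib count | Placebo count | Difference (points) | Ratio |
|---|---|---|---|---|
| 1.00 | 6.0 to 10.0 | 1.50 to 2.50 | 5.00 | 2.0 |
| 0.75 | 4.5 to 7.5 | 1.13 to 1.88 | 3.75 | 2.0 |
| 0.50 | 3.0 to 5.0 | 0.75 to 1.25 | 2.50 | 2.0 |
| 0.25 | 1.5 to 2.5 | 0.38 to 0.63 | 1.25 | 2.0 |

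With unequal capture the ratio can move either way. For c = 0.4 versus 0.6 it is (0.10 × 0.4)/(0.05 × 0.6) = 1.33. For c = 0.6 versus 0.4 it is (0.10 × 0.6)/(0.05 × 0.4) = 3.0. The table covers missed events only. Changes counted near an AE but not caused by a pressure change add to both columns by an unknown amount.

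**The case against.** The protocol says the change must be due to blood pressure but not how to establish this, so the SAP had to supply a rule. An AE plus a 30-day link is prespecified and reproducible. Protocol 8.1 asks for an AE when an intervention is required, so c may be near 1 and little would be lost. Safety is descriptive only (SAP 3.5), so no test is affected. All of this stands. It limits the size of the problem but does not explain why a condition absent from Protocol 9.2.2.1 is undeclared.

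Four stronger readings are tempting, and the documents do not support them.

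- *The clause in Protocol 8.1.4 forbids an AE condition in the final tables.* That clause concerns DSMB monitoring under a charter not included here, and the same section names the AE database as a source.
- *The blood pressure findings as a whole depend on AE reporting.* SAP 3.5.4 has AE-free pressure summaries and an AE-free new-starter count, and vital signs are listed.
- *The ESI will be under-counted.* No capture rate is given, and accepting a change of any kind can over-count.
- *A known pressure effect of the drug class is at stake.* The documents describe none. Protocol 1.4.1 reports no clinically significant vital-sign changes in earlier studies.

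**Conclusion.** The point holds in a limited form. For participants on antihypertensives at Baseline, SAP 3.5.2 narrows a protocol-defined ESI by requiring a listed AE, and SAP section 6 does not say so. Pressure-driven changes without such an AE can be missed, and the changes that are counted mix escalations with reductions and switches. No other planned output counts medication changes in this group.

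The effect cannot be sized from the documents. It is nil on the missed side if every pressure-driven change carries a qualifying AE. Otherwise, with equal capture and no spurious counts, the counted risk difference shrinks in proportion to c and the ratio is unchanged. With unequal capture or spurious counts, the net direction is open. The matter concerns one descriptive count and does not touch the efficacy analysis. It is still worth correcting before lock, because the stated rule can leave out events that the protocol defines as ESIs.

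**What to change.** In SAP 3.5.2, add an AE-independent count by treatment group. It would cover participants on antihypertensives at Baseline, whether or not hypertension is in their medical history, who have any antihypertensive addition, dose increase, dose decrease or stop after first dose. Take it from the concomitant medication data, which Protocol 5.6.3 has recorded at every visit and for which SAP 3.3.6 describes start and stop dates. Show escalations and de-escalations separately. Attribute each change to blood pressure, or not, in a blinded review before lock, using the recorded indication and the visit blood pressures. Keep the AE-linked rule as a sensitivity count. Declare the difference from Protocol 9.2.2.1 in SAP section 6.

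The cost is one extra table and a short blinded review. Some counted changes may not be pressure-driven, which is why the review and the sensitivity count are kept. The documents do not say whether an indication is recorded for every medication; where it is not, attribution rests on the visit pressures. No new CRF field is needed, and clinical care is unaffected.

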- A $>25\%$ decrease in eGFR from Baseline or an eGFR < 30 mL/min/1.73 m², calculated using the Chronic Kidney Disease Epidemiology Collaboration equation, and/or an increase in serum creatinine of ≥ 0.3 mg/dL (≥ 26.5 μ mol/L) from Baseline;
- Changes to antihypertensive medication(s) due to changes in blood pressure in those participants receiving antihypertensive medication(s) treatment at Baseline and those participants not receiving antihypertensive medication(s) treatment at Baseline; and
- Macular degeneration.

An overview of ESIs described above will be provided including counts, percentages of participants by treatment group, and a listing of each ESI.

Values and changes from baseline will be summarized for ALT, AST, and total bilirubin by visit and treatment group. The number and percent of participants with abnormal values for ALT, AST, and total bilirubin will be summarized. These summaries of participants with abnormal values will be performed overall; by normal Baseline; and by abnormal Baseline for ALT, AST, and total bilirubin individually. Hy's Law criteria ($>3 \times \text{ULN}$ for either ALT or AST, with accompanying total bilirubin $>2 \times \text{ULN}$) will also be applied to the data. Any potential Hy's Law cases will be listed separately.

Values and changes from Baseline will be summarized for CK levels by visit and treatment group and visit. In addition, the number and percent of participants with abnormal CK values will be summarized. These summaries of participants with abnormal CK values will be performed overall, by normal Baseline CK, and by abnormal Baseline CK. Values of CK from Baseline to EOT will be summarized by treatment group and by Baseline eGFR category.

Cases of NODM will be recorded and summarized using the appropriate system organ class. These events will be summarized by severity and relationship to study drug for each treatment group. Fasting plasma glucose and HbA1c will be monitored as specified in [Table 1 Schedule of Procedures](#).

Baseline eGFR will be summarized by treatment group for actual value and for Baseline eGFR categories. Shift tables of eGFR category from Baseline to EOT will be provided by treatment group. Shift tables of urine albumin-creatinine ratio and urine protein-creatinine ratio from Baseline to EOT will be provided by treatment group.

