APPENDIX B: PREFERRED TERMS FOR HYPERTENSION

Preferred Term
Accelerated hypertension
Blood pressure ambulatory increased
Blood pressure diastolic increased
Blood pressure inadequately controlled
Blood pressure increased
Blood pressure orthostatic increased
Blood pressure systolic increased
Diastolic hypertension
Essential hypertension
Hypertension
Malignant hypertension
Mean arterial pressure increased
Systolic hypertension
Blood pressure abnormal
Blood pressure ambulatory abnormal
Blood pressure diastolic abnormal
Blood pressure orthostatic abnormal
Blood pressure systolic abnormal
Labile blood pressure
Hypertensive crisis
Hypertensive emergency
Hypertensive urgency
Orthostatic hypertension

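### The SAP's antihypertensive-change rule pools dose cuts and stops with intensification and sets no order between the change, the event and first dose, so a descriptive safety count can misclassify changes as responses to blood pressure

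*SAP*

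**What the plan says.** Protocol 8.1.4 and SAP 3.5.2 both define the event of special interest by cause. The SAP wording is "Changes to antihypertensive medication(s) due to changes in blood pressure in those participants receiving antihypertensive medication(s) treatment at Baseline", which the SAP extends to participants untreated at Baseline. The definition names no direction.

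SAP 3.5.2 then gives an attribution rule for the treated group:

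- **Who:** those who "had a diagnosis of hypertension in their medical history and received antihypertensive medication(s) at Baseline".
- **Trigger:** "If participants had an adverse event related to hypertension after Baseline", using the preferred terms in SAP Appendix B.
- **Qualifying change:** the participant "had any change in antihypertension medication within 30 days of the start date of the adverse event".
- **Consequence:** the change "in antihypertension medication will be considered as due to a change in blood pressure".

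The companion rule, for participants with neither a hypertension diagnosis nor treatment at Baseline, requires that they "initiated antihypertension medication within 30 days of the start date of the adverse event". Protocol 8.1.4.5 has a clinician review each change in participants treated at Baseline, among other things "to assess for etiologies of blood pressure change". The SAP rule does not use that review.

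**The concern.** The event is causal, but the rule that implements it tests neither direction nor order. Two consequences follow.

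- **Direction.** A stop or dose cut near a hypertension event is added to the same count as a new drug or a higher dose. These are opposite responses, and one total cannot show which occurred.
- **Order.** The 30 days are not said to run forward from the event. Suppose a drug is stopped on Day 20 for an unrelated reason and a raised-pressure event starts on Day 35. The stop is 15 days from the event and qualifies on the literal wording, although it came first and may explain the rise.

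Protocol 9.2.4 and SAP 4 both name blood pressure and events of special interest as items for unblinded safety monitoring. SAP 3.5.4 reports the same count again under vital signs. A reader of those tables would want to know what the number measures.

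**Working it through.** The plan states no figure for this rule, so there is none to reproduce. The check is textual, followed by day counting.

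**Is the missing limit supplied elsewhere?** No. Other SAP rules show that such limits can be written:

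| Place in the SAP | Direction stated? | Timing stated? |
|---|---|---|
| 3.5.2, treated at Baseline | No, any change | Within 30 days; no order; only the event must follow Baseline |
| 3.5.2, untreated at Baseline | Yes, initiation | Within 30 days; no order |
| 3.5.2, worsening glycemic control | Yes, new or increased treatment | Not by window |
| 3.5.4, untreated at Baseline | Yes, starts | Yes, confined to the treatment period |

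The group already on treatment has the loosest rule.

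**Window.** From 30 days before to 30 days after the event start is 30 + 1 + 30 = 61 days. Of these, 30/61 = 49% precede the event. A forward window has 31 days.

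**Reach before first dose.** SAP 3.1.1 makes first dose Day 1, with no Day 0. For an event on Day d, the pre-dose days in the window number 30 − (d − 1) = 31 − d, or none if that is not positive:

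- Day 2: 29
- Day 10: 21
- Day 20: 11
- Day 30: 1
- Day 31 onward: 0

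If event starts were uniform over about 400 days (365 of treatment plus 35 of follow-up; uniformity is an assumption), 30/400 = 7.5% of events would be exposed. This is the smallest part of the point.

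**Chance inclusion, for illustration only.** The documents give no rate of unrelated antihypertensive changes. Assume a Poisson rate r per participant-year. The chance of at least one unrelated change in w days is 1 − exp(−r × w/365.25).

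| r (assumed) | 61 days | 31 days | Difference (points) |
|---|---|---|---|
| 0.1 | 1.7% | 0.8% | 0.8 |
| 0.25 | 4.1% | 2.1% | 2.0 |
| 0.5 | 8.0% | 4.2% | 3.9 |
| 1.0 | 15.4% | 8.1% | 7.2 |

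Differences use unrounded values. Each is the chance of being counted only because of a change before the event. The denominator is treated hypertensives who also have an Appendix B event. If 30 of the 300 participants were in that group (assumption), the excess would be 30 × 0.8% to 30 × 7.2%, about 0.2 to 2.2 participants over both arms. Stops that themselves cause the event are not in this model and would add to it.

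**Partial dates.** SAP 3.1.8 imputes a missing start day as the first of the month. Take an event on 15 March and a drug added in March, day unknown. The imputed start is 1 March, 14 days before the event. A forward window of 15 March to 14 April would drop this possible true response if the imputed date were used.

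**The case against.** The strongest reply is that the SAP is silent on order and does not instruct anyone to count earlier changes. It names the event first and then the change attributed to it, so a forward reading is natural. The treated group is identified at Baseline, which suggests a change from the Baseline regimen. SAP 7 leaves detail to separate programming specifications. This stands as a limit: a reader might infer that the plan deliberately counts changes made before the event or before first dose, and the documents do not say so. They only fail to exclude them. Direction is different, because any change is the rule's express wording.

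A second reply is that counting both directions matches a direction-neutral definition. That is right, and reductions should not be deleted. It does not justify showing only the sum.

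Third, safeguards exist. SAP 3.5.2 lists each event of special interest, SAP 3.3.6 lists concomitant medications, and SAP 3.5.4 summarizes blood pressure directly, with thresholds and rises from Baseline. These allow case review and mean that this count is not the only detector. A reader might infer that its purpose is to reveal a rise masked by added drugs. Neither document gives that purpose, and the DSMB charter, which may set its own definition, is not available.

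Fourth, one might fault Appendix B because 6 of its 23 terms carry no direction (five for abnormal readings, such as "Blood pressure abnormal", and one for labile pressure) and none denotes low pressure. The list is titled as a hypertension list, so the absence of low-pressure terms is by design and needs no redesign.

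Finally, a strict forward window can lose true responses through imputed dates or late-recorded onset. This is correct, and the fix has to allow for it.

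**Conclusion.** The point holds for the rule covering participants treated at Baseline. As written, it pools opposite changes and leaves room to count a change that preceded the event as a response to it. The pooling is explicit; the order and pre-dose parts rest on literal wording and silence, and the pre-dose part concerns only events starting by Day 30.

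The consequence is misclassification in one descriptive safety count. The rule is the same in both arms, and SAP 3.5 applies no inference to safety endpoints, so a reader should not infer a bias in any test or in the efficacy results. The size cannot be derived from the documents; the illustrative excess rests wholly on assumed rates and an assumed number of eligible participants. The change is still worth making before unblinding, because it costs little and gives the count a clear meaning.

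**What to change.** In SAP 3.5.2, for participants treated at Baseline:

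1. Count a change only if it is dated on or after first dose and falls from the event start date to 30 days after it.
2. Tabulate by arm intensification (new drug or higher dose) separately from reduction or stop. Keep the total, since the event definition is direction-neutral.
3. Where a change date is partial, do not use the imputed first-of-month date to exclude it. Keep the change if its possible dates overlap the window; the March example above would then be kept.
4. Show changes dated before the event in the listing, flagged as such.

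The count repeated in SAP 3.5.4 should follow the same rule. The cost is SAP wording and programming on medication and event data already collected, assuming that the case report form captures antihypertensive doses well enough to classify a change as up or down. The downside is that a responsive change dated just before a late-recorded onset moves from the count to the listing. Forward-only counting also does not remove coincidence: under the assumed rates it roughly halves it.

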9.2.2 Analysis of Safety

The Safety Population will be the primary population for the safety analysis. All safety endpoints will be summarized descriptively. No statistical inference will be applied to the safety endpoints.

AEs will be categorized by primary system organ class and preferred term as coded using the Medical Dictionary for Regulatory Activities category designations. Summaries of AEs, including the number and percentage of participants who experience an AE, will be provided.

Laboratory values will be summarized descriptively, including the change from Baseline, by treatment group, and overall. In addition, shift tables will be presented to describe the change in laboratory parameter values at post-Baseline visits using normal range categories (low, normal, and high).

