6 CHANGES FROM PROTOCOL-SPECIFIED STATISTICAL ANALYSES

There have been four changes from the protocol v3.0.

The first change is in the description of the study objectives and endpoints, the term 'fasting' from version 3.0 of the protocol, which precedes the specified lipid parameter, has been removed. The Schedule of Procedures, along with Section 8.7 of the protocol, specifies that all laboratory samples should be collected while the participant is fasting; therefore, the corresponding language was removed from the objective and endpoint descriptions in the SAP. Additionally, the primary efficacy endpoint for the LDL-C assessment will utilize values collected via preparative ultracentrifugation (PUC), also referred to as beta quantification, which is not sensitive to fasting status.

The second change is the inclusion of subgroup analysis.

The third change is the inclusion of the evaluation of trough levels of obicetrapib from Baseline to Day 84 and 180 in the obicetrapib group.

The fourth change is the change in the variance for the primary analysis. The model will assume unequal variances for each treatment group. Therefore, supportive analysis of the primary efficacy assessment will not require consideration of an ANCOVA model assuming unequal variances, as described in v3.0 of the protocol.

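### SAP 3.5.3 limits laboratory shift tables to the end of treatment visit, where the protocol specifies post-Baseline visits, and SAP Section 6 does not declare the change

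*SAP*

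**What the plan says.** Protocol 9.2.2, repeated in the synopsis, says that "shift tables will be presented to describe the change in laboratory parameter values at post-Baseline visits using normal range categories" of low, normal and high. SAP 3.5.3 says that "shift tables for all parameters will be presented to describe the change in laboratory parameter values at end of treatment visit", with the same three categories.

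SAP Section 6 opens with "There have been four changes from the protocol v3.0" and names them: dropping the word fasting from objectives and endpoints, adding subgroup analyses, adding trough levels at Days 84 and 180, and fitting unequal variances in the primary model. The shift tables are not mentioned.

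Other laboratory outputs in SAP 3.5 carry no end-of-treatment restriction. On events of special interest: "An overview of ESIs described above will be provided including counts, percentages of participants by treatment group, and a listing of each ESI". On liver tests: "The number and percent of participants with abnormal values for ALT, AST, and total bilirubin will be summarized". On CK: "the number and percent of participants with abnormal CK values will be summarized". On laboratory data in general: "Laboratory values will be summarized descriptively, including the change from Baseline".

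**The concern.** The protocol's plural does not look like loose wording for end of treatment. Where the protocol wants a shift from Baseline to EOT only, it says so: Protocol 9.2.2.1 does this for eGFR category and for the two urine ratios. The SAP applies that narrower form to every laboratory parameter without recording it as a change.

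The shift table also has a specific job. Protocol 8.7.4 keeps out-of-range results that do not meet its clinical-significance criteria off the adverse event form, on the footing that they will be analyzed and reported as laboratory abnormalities. For an analyte with no ESI threshold and no abnormal-value count, the shift table is the only SAP output that counts participants by normal-range category. If it covers one visit, such a result at any earlier visit enters no count by arm. Safety is a secondary objective, and the sample size section cites exposure and safety data as part of its justification.

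**Working it through.** There is no stated figure to reproduce. The check compares the texts and counts scheduled draws.

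**1. The two commitments.** Protocol 9.2.2: post-Baseline visits (plural), low/normal/high. SAP 3.5.3: end of treatment visit (one), low/normal/high, all parameters. Section 6: four declared changes, none of them this one. The narrowing is real and undeclared.

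**2. What stays counted without the earlier-visit shift tables (SAP 3.5.2).**
- ESI counts and percentages: ALT or AST above 3×ULN, total bilirubin above 2×ULN, CK above 5×ULN, the HbA1c and fasting glucose criteria, and the eGFR and creatinine criteria.
- Abnormal-value counts, overall and by normal or abnormal Baseline: ALT, AST, total bilirubin and CK.
- A Hy's Law screen.

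Glucose, HbA1c, creatinine and eGFR are therefore covered by threshold, though not by normal-range category. The analytes with neither kind of count include alkaline phosphatase, gamma-glutamyl transferase (GGT), the other full-panel chemistry, hematology and coagulation.

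**3. Share of scheduled post-Baseline draws that an EOT-only table uses.** The panels come from Protocol Appendix B. The visits come from SAP Table 1 and the design text on the End of Study (EOS) visit. The full panel is drawn at Days 180 and 365, and the limited panel at Days 30, 84, 270 and EOS. Share = EOT draws ÷ all scheduled post-Baseline draws.

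| Analytes | Post-Baseline draws | Share used | Without EOS |
|---|---|---|---|
| Alkaline phosphatase, GGT (both panels) | Days 30, 84, 180, 270, 365, EOS | 1/6 | 1/5 |
| Full panel only (e.g. electrolytes, albumin, uric acid) | Days 180, 365 | 1/2 | 1/2 |
| Hematology, coagulation | Days 180, 365, EOS | 1/3 | 1/2 |
| Urinalysis | Day 365 | 1/1 | 1/1 |

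The last column is given because EOS falls about 35 days after the last dose.

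**4. Early terminators.** Under Protocol 4.3 the ET visit has the same procedures as the EOT visit, so a sample should exist. SAP 3.1.2, Table 2, assigns ET visits by analysis day, and only Day 318 onward maps to Day 365 (EOT). An ET sample on Day 200, for example, falls in the 133–225 window and becomes a Day 180 value. Two readings of the SAP's end of treatment visit follow:
- The participant's actual EOT or ET sample: the early terminator is in the table.
- Analysis visit Day 365 (EOT): anyone whose ET visit is before Day 318 is not.

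SAP 3.5.3 does not say which applies.

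**The case against.** The case for leaving this as a minor wording matter has force. A reader might infer that transient abnormalities vanish from the safety tables. They do not:
- The ESI counts and the liver and CK abnormal-value counts cover the main laboratory signals at any visit.
- Clinically significant results are recorded as adverse events under Protocol 8.7.4 and so reach the adverse event tables.
- Continuous summaries include minimum and maximum (SAP 3.1.5), and SAP Section 7 promises participant listings of all available data.
- An independent board reviews unblinded safety data about every six months (SAP Section 4).

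Three further inferences are tempting, and the documents do not support them:
- That an EOT-only table catches one fifth of transient abnormalities across the board. Most of the affected analytes are drawn two or three times after Baseline, and a detection probability would also need an assumption about when abnormalities occur.
- That about 15 participants (5% of 300) would be missing. The 5% is a planning assumption about evaluability for efficacy, and early leavers are scheduled for an EOT-type sample.
- That the protocol promised every post-Baseline visit, or a worst-value table. It says neither.

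These points limit the size of the loss but do not remove the mismatch. Summary statistics and listings give no count by arm of participants who moved out of range, and the adverse event route excludes by design the results that Protocol 8.7.4 leaves to laboratory reporting.

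**Conclusion.** The point holds as an undeclared narrowing of a protocol-specified safety output. The loss is confined to low/normal/high counts by arm, before end of treatment, for analytes without an ESI threshold or abnormal-value count. The table uses 1 of 6 draws for alkaline phosphatase and GGT, 1 of 2 for full-panel-only chemistry, and 1 of 3 for hematology and coagulation. Urinalysis is unaffected, and the eGFR category and urine ratio shifts follow the protocol as they stand.

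The possible omission of early terminators depends on how end of treatment visit is read, and the number affected cannot be derived from the documents. The draw counts assume the visit placement in SAP Table 1 together with the EOS description, and they count scheduled samples only. Safety reporting here is descriptive, without inference, and no efficacy result depends on it. The change should be made, but the trial's conclusions on efficacy do not turn on it.

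**What to change.** In SAP 3.5.3, restore the normal-range shift tables by scheduled post-Baseline visit, as in Protocol 9.2.2. State that the end-of-treatment shift uses the participant's actual EOT or ET sample, whatever analysis visit Table 2 assigns to it, so that early terminators are kept. A shift from Baseline to the worst post-Baseline value would be a useful optional addition, but the protocol does not promise it.

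The cost is a few lines of SAP text and extra table output from data already being collected. No new samples are needed, and the efficacy analyses do not change.
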